Appendix 4. Lifestyle Guidelines for Subjects from Sites in Sweden and the United Kingdom

All female subjects who are of childbearing potential and are sexually active and at risk for pregnancy, and **who withdraw from Study A4091056, A4091057 A4091058, or other tanezumab study less than 16 weeks after the last dose of subcutaneous** investigational product must agree to use one (1) method of highly effective contraception consistently and correctly **until 112 days (16 weeks) after the last dose of subcutaneous** investigational product. The investigator or his/ or her designee, in consultation with the subject, will confirm the subject has selected the most appropriate form of contraception for the individual subject from the permitted list of contraception methods (see below), and instruct the subject in its consistent and correct use. Subjects need to affirm that they meet the criteria for correct use of the selected method of contraception. The investigator or his/her designee will discuss with the subject the need to use highly effective contraception consistently and correctly according to the schedule of activities and document such conversation in the subject's chart. In addition, the Investigator or his/ or her designee will instruct the subject to call immediately if the selected birth control methods are discontinued or if pregnancy is known or suspected in the subject.

Highly effective methods of contraception are those that, alone or in combination, result in a failure rate of less than 1% per year when used consistently and correctly (ie, perfect use) and include the following:

1. Established use of hormonal methods of contraception is allowed provided the subject remains on the same treatment throughout the entire study and has been using that hormonal contraceptive for an adequate period of time to ensure effectiveness. Acceptable methods include:
 - Combined (estrogen and progestogen-containing) hormonal contraception associated with inhibition of ovulation:
 - Oral
 - Intravaginal
 - Transdermal
 - Progestogen-only hormonal contraception associated with inhibition of ovulation¹:
 - Oral
 - Injectable
 - Implantable

2. Correctly placed intrauterine device (IUD) or intrauterine hormone-releasing system (IUS).
3. Bilateral tubal occlusion.
4. Vasectomized partner provided that the partner is the sole sexual partner of the trial participant and that the vasectomized partner has received medical assessment of the surgical success.
5. Sexual abstinence, defined as refraining from heterosexual intercourse during the entire period of risk associated with the study treatments. The reliability of sexual abstinence needs to be evaluated in relation to the duration of the clinical trial and the preferred and usual lifestyle of the subject.

There are no contraception requirements for sexually active female subjects of childbearing potential who withdraw from Study A4091056, A4091057, A4091058 or other tanezumab study more than 16 weeks after the last dose of subcutaneous investigational product.

1. Progestogen-only oral hormonal contraception where inhibition of ovulation is not the primary mode of action is not acceptable as a highly effective method.

Source: Clinical Trial Facilitation Group. Recommendations related to contraception and pregnancy testing in clinical trials [Internet]. Germany: Heads of Medicines Agencies (HMA); 2014 [2014 Sep 15; cited 2015 Aug 12]. Available from: http://www.hma.eu/fileadmin/dateien/Human_Medicines/01-About_HMA/Working_Groups/CTFG/2014_09_HMA_CTFG_Contraception.pdf.

1. AMENDMENTS FROM PREVIOUS VERSION(S)

This is the third amendment to the previously approved SAP (version 3.0 on 29Mar2019). Summary of changes of this amendment versus the previously amended SAP (version 2.0) include:

- Updated the analysis of additional or corrective procedure, post-surgical complications, AE special interest, adjudicated outcome, under Section 6 and 8.2.1,
- Updated subgroup analysis (removed by age, gender, BMI, KL grade, number of joint of OA and added sub-population for subjects who had RPOA, Primary ON, SIF or NPOA for three endpoints) under Section 6.3, and Section 8.2.1. The first group of subgroup analyses are recognized as less informative due to small N based on the discussion with clinical. Subgroups were added for considering joint safety outcomes of parent studies regardless of the number of subjects.
- Updated summary of analysis based on the discussion with team under Section 8.2.2.

This is the second amendment to the previously approved SAP (version 2.0 on 19June2018). Summary of changes of this amendment versus the previously amended SAP (version 2.0) include:

- Clarified the status of patients from A4091059, A4091061 and A4091063 under Section 2.2,
- Changed the name of clinical research organization name from “inVentiv” to “Syneos” due to integration of the companies under Section 3,
- Changed the definition of analysis set from Full Analysis Set to Safety Analysis Set with considering endpoint characteristics under Section 5, and Section 8,
- Updated preferred term of adverse events about the abnormal peripheral sensation, and the sympathetic nervous system under Section 6.1,
- Updated analysis methodology under Section 8,
- Updated total joint replacement and adjudicated outcome under Section 8.1.3,
- Added subpopulation summary table about RPOA (type 1 and type 2), RPOA (type 1), RPOA (type 2), Primary ON, SIF and NPOA under Section 8.2.1, and removed all other subgroup analysis under Section 8.2.1 and 8.2.2,
- Updated summary of analysis (Section 8.2.2) based on above section

This is the first amendment to the previously approved SAP (version 1.0 on 01October2015). Summary of changes of this amendment versus the previously amended SAP (version 1.0) include:

- Amended the possibility of adverse events summarize of decreased sympathetic function under Section 8.2.1.
- Added to summarize for combined all osteoarthritis studies for our clarity under Section 8.
- Added the unblinding plan related to section 5 of A4091064 protocol under Appendix 2 of this document.

2. INTRODUCTION

Note: in this document any text taken directly from the protocol is *italicised*.

2.1. Study Design

This is a Phase 3, multicenter, long-term observational study of subjects from tanezumab Study A4091056, A4091057 or A4091058 (regardless of treatment group) who undergo a total knee, hip or shoulder replacement during participation in the study (treatment period or safety follow-up period). If while the subject is participating in this study (A4091064), the subject undergoes an additional total joint replacement surgery or the site becomes aware that an additional total joint replacement surgery has been scheduled for the subject, the subject will be requested to provide information on the additional total joint replacement surgery as well. Finally, any subject with a qualifying total joint replacement after the last subject in the study completes the treatment period in studies A4091059, A4091061 or A4091063 may be followed in this study (A4091064). However, due to change of the enrolment strategy, patients will not be enrolled from A4091061 and A4091063. In addition, patients were not enrolled from A4091059. The patients with TJR in these three studies will be summarized within each individual study or be listed if there are too few to summarize.

This study is designed with a total duration of subject follow-up of 24 weeks after the total joint replacement surgery.

Following the surgery, the subject will be contacted monthly via telephone by study site personnel to ascertain whether the subject has experienced any adverse events and to record any concomitant analgesic medications the subject is taking as well as the reason for the medication use. An assessment of the subject's overall satisfaction with their total joint replacement (Interactive Web-Response System, IWRS), average pain in the replaced joint (IWRS), the subject's level of function and activity in the replaced joint (IWRS) and physical rehabilitation activities (telephone interview) will be made at Weeks 4, 12 and 24. At Weeks 12 and 24, subjects will be queried during the telephone interview as to whether any additional or corrective procedures related to the total joint replacement are planned.

All events of total knee, hip or shoulder replacement will be reviewed by the Joint Safety Adjudication Committee (Adjudication Committee) established for the tanezumab clinical program. This Committee will adjudicate in an independent and blinded fashion if the event is primary osteonecrosis, worsening OA (further sub-divided into rapidly progressive OA [RPOA] type 1 or type 2, normal progression of OA or not enough information to distinguish between RPOA and normal progression of OA), subchondral insufficiency fracture, pathologic fracture, other (with diagnosis specified) or not enough information to specify a diagnosis.

2.2. Study Objectives

Primary Objective:

- *To describe the post-operative outcome of subjects who underwent a total knee, hip, or shoulder replacement while participating in tanezumab Study A4091056, A4091057 or A4091058 (treatment period and safety follow-up period).*

Secondary Objectives:

- *To compare the post-operative outcome for tanezumab 2.5 mg and 5 mg versus non-steroid anti-inflammatory drugs (NSAIDs) for subjects who underwent a total knee, hip, or shoulder replacement while participating in tanezumab Study A4091058.*
- *To describe the post-operative outcome of subjects from the A4091059, A4091061 or A4091063 studies who underwent a total knee, hip, or shoulder replacement*

3. INTERIM ANALYSES, FINAL ANALYSES AND UNBLINDING

The final analysis for this study will be performed after the database has been released.

The incidence of subjects with total joint replacements, and resulting adjudicated outcomes will be summarized throughout the tanezumab program. This includes the parent studies of this protocol (A4091056, A4091057, and A4091058), this study itself, and other tanezumab studies (A4091059, A4091061, and A4091063). These analyses will be produced for the Data Monitoring Committee (DMC) and will be unblinded to the DMC members. These analyses will be produced by a separate unblinded group at Syneos who are separate from the corresponding study team at both Syneos and Pfizer.

Information from this study will be blinded for the parent study treatment group until the parent study itself has been unblinded.

In all cases the adjudication of joint safety events is made in a blinded fashion by the adjudication committee.

Interim analyses of these data may be produced for inclusion in a regulatory submission. In this case, a snap-shot of the database will be taken and stored. If this interim analysis occurs, then all parent study databases would have been finalized and those studies unblinded, therefore it is not envisioned that subjects would be unblinded due to this interim analysis.

4. HYPOTHESES AND DECISION RULES

4.1. Statistical Hypotheses

There is no given sample size for this study, both for the overall number of subjects and for the number of subjects in any single (parent study) treatment group. Data will be summarized overall and then by parent study and parent study treatment group. Given the likely lack of statistical power for treatment comparisons, no inferential testing will be performed, and all summaries and analyses will be descriptive in nature.

4.2. Statistical Decision Rules

There will be no statistical inferential testing in this study.

5. ANALYSIS SETS

5.1. Full Analysis Set

Not Applicable.

5.2. ‘Per Protocol’ Analysis Set

There will be no per-protocol analysis set defined for this study.

5.3. Safety Analysis Set

The ‘Safety Analysis Set’ (SAS) is the analysis set for all analyses. It consists of all treated subjects who enrolled in Study A4091064, and who have a qualifying total joint replacement for Study A4091064. This analysis set is used in the presentations of all data summaries and listings and is labeled as the ‘Safety Analysis Set’ or ‘SAS’.

5.4. Other Analysis Sets

No other analysis sets are defined.

5.5. Treatment Misallocations

Parent study treatment allocation will be based on the actual treatment group received. Where a subject received an incorrect treatment (versus the planned treatment group as required by the randomisation procedure) then the subject will be allocated to a treatment group received where this matches a treatment group from that study or other studies, ie, from the following list:

- Placebo SC;
- Tanezumab 2.5mg;
- Tanezumab 2.5/5mg (tanezumab 2.5mg at Baseline and tanezumab 5mg at Week 8);
- Tanezumab 5mg;
- Tanezumab 10mg;
- NSAID (with placebo SC);
- Tramadol (with placebo SC).

Where the subject's actual treatment does not match one of the groups listed above, then the subject will be allocated to a treatment group based on the highest dose of tanezumab received (eg, if a subject received placebo SC at Baseline and tanezumab 5mg at Week 8 the subject would be allocated to the tanezumab 5mg group).

5.6. Protocol Deviations

Given this is an observational safety study and there is no per-protocol analysis set being used, then no deviations for the purpose of analyses will be defined.

5.6.1. Deviations Assessed Prior to Randomization

Not applicable.

5.6.2. Deviations Assessed Post-Randomization

Not applicable.

6. ENDPOINTS AND COVARIATES

6.1. Endpoints

Given the design of this study, the following endpoints are considered co-equal:

- *Surgeon's Assessment of Procedural Difficulty: number and percentage of surgeries assessed as uneventful, minor complications or major complications.*
- *Subject's overall satisfaction with surgery as assessed by the Self-Administered Patient Satisfaction (SAPS) Scale: number and percentage of subjects satisfied vs. unsatisfied with their total joint replacement at Week 24.*
- *Number and percentage of subjects with a post-surgical complication(s) up to Week 24 (derived from reported adverse events).*
- *Number and percentage of subjects with additional or corrective procedures related to their total joint replacement up to Week 24.*
- *Number and percentage of subjects participating in physical rehabilitation activities related to the replaced joint up to Week 24.*
- *Change from Baseline to Week 24 in average pain in the replaced joint.*
- *Change from Baseline to Week 24 in WOMAC Pain, Stiffness and Physical Function subscales in the replaced joint (subjects undergoing total hip or knee replacement surgery only).*
- *Change from Baseline to Week 24 in the Shoulder Pain and Disability Index (SPADI) in the replaced shoulder (subjects undergoing total shoulder replacement surgery only).*

- *Concomitant analgesic medication use.*

The WOMAC subscale scores of Pain, Stiffness and Physical Function are calculated as the mean of the 5, 2 and 17 items, respectively, from the WOMAC questionnaire. Each item is scored on a 0-10 numerical rating scale (NRS), and so the WOMAC subscale scores themselves have a range of 0-10, with 0 being the best response.

The Average Pain in the replaced joint will be scored on a 0-10 NRS scale, where 0 is ‘no pain’ and 10 is the ‘worst possible pain’.

The Self-Administered Patient Satisfaction (SAPS) contains the following four questions:

- *How satisfied are you with the results of your surgery?*
- *How satisfied are you with the results of your surgery for improving your pain?*
- *How satisfied are you with the results of surgery for improving your ability to do home or yard work?*
- *How satisfied are you with the results of surgery for improving your ability to do recreational activities?*

Items are scored on a 4-point Likert scale with response categories consisting of ‘very satisfied’ (100 points), ‘somewhat satisfied’ (75 points), ‘somewhat dissatisfied’ (50 points), and ‘very dissatisfied’ (25 points). The scale score is the unweighted mean of the scores from the individual items, ranging from 25 to 100 per item with higher scores indicating greater satisfaction.

The SPADI consists of two dimensions (pain and function). The pain dimension consists of five questions regarding the severity of an individual’s pain. Functional activities are assessed with eight questions designed to measure the degree of difficulty an individual has with various activities of daily living that require upper extremity use. The scores from both dimensions are averaged to derive a total score from 0 (best) to 100 (worst). The pain dimension is calculated as the sum of non-missing scores divided by the maximum possible score (50 with no missing items) multiplied by 100. The disability (function) dimension score is calculated as the sum of non-missing scores divided by the maximum possible score (80 with no missing items) multiplied by 100. The dimension scores can be calculated with up to 2 missing items, however if there are >2 missing items from a dimension then that dimension cannot be scored, and is set to missing. A SPADI total score will be calculated as the mean of the pain and disability (function) dimensions.

The Surgeon’s Assessment of Procedural Difficulty asks the question “*Taking into consideration the subject’s medical history and physical condition prior to surgery would you classify the operative procedure as*” with the following three possible outcome categories:

- Uneventful;
- Minor complications;
- Major complications.

In the case of any complications the surgeon is then asked to specify the complication.

At the Week 12 and 24 post-surgery telephone contacts, subjects will be queried for additional or corrective procedures related to the total joint replacement surgery. Specifically, subjects will be asked to respond yes or no to the following question:

- *Have you been told by your orthopedic surgeon that additional or corrective procedures (for example a revision or implant replacement) are necessary for your total joint replacement?*

Subjects will be queried for details if the answer to the question is yes.

At the Week 4, 12 and 24 post-surgery telephone contacts, subjects will be queried for rehabilitation activities related to the replaced joint. Specifically, subjects will be asked to respond yes or no to the following question:

- *Are you participating in physical rehabilitation activities related to your replaced joint?*

Subjects will be queried for details if the answer to the question is yes.

The data relating to the endpoints of physical rehabilitation, or additional or corrective procedure, related to the replaced joint up to Week 24 will be derived from an ongoing clinical review of the concomitant non-drug treatment/procedure case report form (CRF) page. This review will identify treatments that are relevant for these endpoints, and a log of such data will be maintained. The data relating to the endpoint of concomitant analgesic medication use will be derived from an ongoing review of the concomitant analgesic drug CRF page. These reviews will be made during the study and data will be finalized prior to the database release for this study.

Events identified as the first symptom leading to total joint replacement will be reviewed and determined prior to the unblinding for the respective parent study.

The list of post-surgical complications will be derived from reported adverse events and will consist of complications that are clinically significant and attributable to the total arthroplasty procedure eg, periprosthetic joint infection/wound infection, periprosthetic fracture, pulmonary embolism or sepsis/septicemia/shock. The list of post-surgical complications will be developed during Study A4091064 and finalized prior to Study A4091058 unblinding. Other adverse events may be identified as post-surgical complications after the unblinding of the Study A4091058 database. These events will also be summarized as complications, and will be noted as having been included in the list after the unblinding of the Study A4091058 database.

Adverse Events which are “treatment emergent” in relation to the Baseline study day will be reported overall and by prior study treatment group. Adverse events ongoing from the parent study will continue to be followed in this study. They will not be included in incidence tables from this study unless the severity worsens.

Groups of the adverse events of abnormal peripheral sensation, sympathetic nervous system and decreased sympathetic function are shown below. These events will be evaluated from overall adverse events summaries if needed.

The preferred terms for adverse events of abnormal peripheral sensation are defined below.

Allodynia	Neuralgia
Axonal neuropathy	Neuritis
Burning sensation	Neuropathy, peripheral
Decreased Vibratory Sense	Paraesthesia
Demyelinating polyneuropathy	Paraesthesia oral
Dysaesthesia	Peripheral sensorimotor neuropathy
Formication	Peripheral sensory neuropathy
Hyperaesthesia	Polyneuropathy
Hyperpathia	Polyneuropathy chronic
Hypoaesthesia	Sensory disturbance
	Sensory loss
Hypoaesthesia oral	Thermohypoaesthesia
Intercostal neuralgia	Carpal tunnel syndrome
Sciatica	Tarsal tunnel syndrome

The preferred terms for adverse events of the sympathetic nervous system are defined below.

Abdominal discomfort	Micturition urgency
Anhidrosis	Nausea
Blood pressure orthostatic decreased	Nocturia
Bradycardia	Orthostatic hypotension
Diarrhea	Presyncope
Dizziness postural	Respiratory distress
Early satiety	Respiratory failure
Ejaculation delay	Sinus bradycardia
Ejaculation disorder	Syncope
Ejaculation failure	
	Urinary hesitation
Heart rate decreased	Urinary incontinence
Hypertonic bladder	Vomiting
Hypohidrosis	Anal incontinence
Pollakiuria	

The preferred terms for adverse events of decreased sympathetic function are defined below.

Anhidrosis	Orthostatic hypotension
Bradycardia	Syncope
Hypohidrosis	

Case Report Forms are available in Study A4091064 to capture results from neurological consultations or sympathetic nervous system consultations. If any such consultations occur, they will be reported overall and by prior study treatment group, as possible.

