6.1. Baseline Visit

Baseline information for this study should be obtained as close as possible to, and prior to, the total joint replacement surgery. The Baseline Visit may coincide with the last visit in Study A4091056, A4091057 or A4091058 (End of Study or Early Termination Visit) or occur when the site is notified of a planned total joint replacement surgery. If a total joint replacement occurs or is scheduled to occur after the last subject in the study completes the treatment period in Study A4091059, A4091061 or A4091063 baseline activities could be conducted at either the end of study visit or at the early termination visit in Study A4091059, A4091061 or A4091063. Baseline Visit activities must be conducted at the clinical site.

Subjects should be queried about their access to the internet via a desktop, laptop or tablet computer so as to determine the appropriate format for the subject reported outcomes of pain in the joint to be (or post-surgery, that has been) replaced, functional status and, post-surgery, satisfaction with surgery.

Subjects with access to the internet via a desktop, laptop or tablet computer should be trained in the use of the ePRO system (IWRS) and in their responsibilities for data entry in compliance with the protocol. IWRS technical support (Help Desk) will be available to the subject for the duration of the study. Beginning with the Baseline Visit, subjects with access to the internet via a desktop, laptop or tablet computer should complete the aforementioned assessments via the IWRS. In the event of internet connectivity issues at the Baseline Visit, paper versions of the assessments should be completed.

Only subjects without access to the internet via a desktop, laptop or tablet computer during Study A4091064 should complete the aforementioned assessments on paper for the duration of Study A4091064. Simple preference for the use of paper is not sufficient to allow its use by the subject who has access to the internet via a desktop, laptop or tablet computer during Study A4091064.

Except in unusual circumstances, subjects should not switch between paper-based and web-based completion of the subject reported outcome measures.

Thorough instruction should be provided for completion of self-administered scales (subject reported outcomes) however, no coaching or other interpretative assistance should be given to the subject during the completion of the questionnaires.

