In addition, the number and percent of subjects with specified post-surgical complications will be presented. The list of post-surgical complications will be derived from reported adverse events and non-drug treatment/procedure. It will consist of complications that are clinically significant and attributable to the total arthroplasty procedure eg, periprosthetic joint infection/wound infection, periprosthetic fracture, pulmonary embolism or sepsis/septicemia/shock. The list of post-surgical complications will be developed during Study A4091064 and finalized prior to Study A4091058 unblinding. Other adverse events may be identified as post-surgical complications after the unblinding of the Study A4091058 database. These events will also be summarized as complications, and will be noted as having been included in the list after the unblinding of the Study A4091058 database.

Adverse events and concomitant analgesic medications will be collected for each subject during the study according to the Schedule of Assessments. Standard safety reporting tables will summarize and list these safety data.

Separate adverse event summaries by parent study treatment group for adverse events of abnormal peripheral sensation, and sympathetic nervous system will be presented. Adverse event summaries of decreased sympathetic function may be presented.

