Post-surgical complications (All OA parent studies)	Any time post-surgery	SAS	None	N/A	Observed	
Concomitant analgesic medication use (All OA parent studies)	Any time post-surgery	SAS	None	N/A	Observed	Summary of surgical outcome
Subpopulation summary of Surgeon's Assessment of Procedural Difficulty for subjects who had RPOA (type 1 and type2), RPOA (type 1), RPOA (type 2), primary ON, SIF, or NPOA	BL, Week 4, 12, 24, 24 (LOCF)	SAS	None	N/A	Observed	Subgroup presentation
Subpopulation summary of Subject's Overall Satisfaction for subjects who had RPOA (type 1 and type2), RPOA (type 1), RPOA (type 2), primary ON, SIF, or NPOA	BL, Week 4, 12, 24, 24 (LOCF)	SAS	None	N/A	Observed	Subgroup presentation

Endpoint	Time points	Analysis Set	Statistical Method	Model/ Covariates/ Strata	Missing Data	Objective
Subpopulation summary of concomitant nondrug treatment for subjects who had RPOA (type 1 and type2), RPOA (type 1), RPOA (type 2), primary ON, SIF, or NPOA	Any time post-surgery	SAS	None	N/A	Observed	Subgroup presentation

SAS: Safety analysis set for subjects with TJR and entered into 1064

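### General adverse event incidence is counted from the pre-surgery Baseline with no split at surgery, so by-arm percentages mix a variable pre-operative wait with the 24 post-operative weeks

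*SAP*

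**What the plan says.** **Anchor.** SAP 6.1 reports AEs that are emergent "in relation to the Baseline study day will be reported overall and by prior study treatment group".

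**Where Baseline lies.** Protocol 6.1 says: "Baseline information for this study should be obtained as close as possible to, and prior to, the total joint replacement surgery". The same section lets the visit coincide with the last parent-study visit, or take place when the site learns of a planned operation. SAP Appendix 1.1 gives Baseline a window with no lower limit that ends at Day -1. Under Protocol 8.2, recording on the A4091064 case report form starts at consent.

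**Parent-study AEs.** SAP 6.1 states: "Adverse events ongoing from the parent study will continue to be followed in this study". It then adds: "They will not be included in incidence tables from this study unless the severity worsens".

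**Post-surgical complications.** The row "Post-surgical complications (All OA parent studies" in SAP 8.2.2 is timed to the post-surgery period.

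**Special-interest groups.** After naming the peripheral-sensation and sympathetic groups, SAP 6.1 says: "These events will be evaluated from overall adverse events summaries if needed". SAP 8.2.1 says: "Separate adverse event summaries by parent study treatment group for adverse events of abnormal peripheral sensation, and sympathetic nervous system will be presented".

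**Denominator.** On the Safety Analysis Set, SAP 5.3 says: "It consists of all treated subjects who enrolled in Study A4091064, and who have a qualifying total joint replacement for Study A4091064".

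**The concern.** The study exists to describe what happens after a joint replacement, and a secondary objective compares tanezumab arms with NSAID. An AE percentage that runs from a pre-surgery day of no fixed distance describes neither the wait nor the post-operative course. It also depends partly on how long each subject waited.

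This matters most for any sympathetic table. The SAP 6.1 list includes nausea, vomiting, urinary hesitation and syncope, which may have different causes before and after an operation. Without a split, such a percentage is hard to read as either a late drug effect or a surgical effect.

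A smaller matter concerns entry. Inclusion criterion 3 in Protocol 4.1 accepts an actual as well as a planned replacement during the parent study. If a subject consented after the operation, a post-operative AE that began in the parent study and was still ongoing would meet the exclusion in SAP 6.1 unless it worsened.

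**Working it through.** The documents state no figure on this point, so there is nothing to reproduce. The check traces the AE window and then illustrates its effect.

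**1. The window.** Surgery is Day 1 and Week 24 is Day 169, so post-surgical follow-up is 169 − 1 = 168 days, or 24 weeks. The AE window is that period plus the wait w from Baseline to surgery. The share of the window before surgery is w/(w + 24). With assumed waits:

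- 4 weeks: 4/28 = 14.3%
- 8 weeks: 8/32 = 25.0%
- 12 weeks: 12/36 = 33.3%

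**2. Tabulated incidence.** Let p be the 24-week post-surgical incidence and r the ratio of the pre-operative to the post-operative AE rate. With constant rates in each period:

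tabulated incidence = 1 − (1 − p)^((24 + r·w)/24)

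For example, with p = 40%, w = 4 and r = 1: 1 − 0.6^(28/24) = 44.9%. All of p, w and r are assumptions. For p = 40%:

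| r | w = 4 | w = 8 | w = 12 |
|---|---|---|---|
| 1 | 44.9% | 49.4% | 53.5% |
| 0.5 | 42.5% | 44.9% | 47.2% |
| 0.25 | 41.3% | 42.5% | 43.7% |

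Over the same grid, an assumed p of 20% is tabulated as 20.7% to 28.4%, and 60% as 61.5% to 74.7%. The lower ratios are plausible, because Protocol 7.3.1 schedules AE queries at the post-surgery contacts.

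**3. Between arms.** Suppose two arms share a true 40% but wait 4 and 8 weeks. The table would show a gap of 49.4 − 44.9 = 4.5 points at r = 1, or 44.9 − 42.5 = 2.4 points at r = 0.5. If waits and pre-operative rates are the same in both arms, this mechanism creates no gap.

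**4. Consent after surgery.** The texts conflict:

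- Criterion 3 admits an operation that has already taken place, and criterion 2 requires that the parent study is over for the subject.
- Protocol Table 1 lists consent among the pre-surgery activities, Protocol 6.1 puts Baseline before the operation, and SAP Appendix 1.1 ends the Baseline window at Day -1.

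A late consenter therefore has no valid Baseline day, and emergence is undefined for that subject. AEs that resolved before consent are not on the A4091064 form, yet the subject stays in the denominator. If consent came 7, 14, 28 or 56 days after surgery (assumed), the share of the post-operative window before recording starts would be 7/168 = 4.2%, 14/168 = 8.3%, 28/168 = 16.7% or 56/168 = 33.3%. The SAP does not say whether parent-study AEs with onset on or after surgery feed the complication summary.

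**The case against.** The case for leaving the plan alone is substantial. General AE incidence is not among the co-equal endpoints. The AE-derived endpoint that addresses post-operative outcome is complications, which is already timed post-surgery, limited to events attributable to the arthroplasty, and also drawn from non-drug treatment and procedure data. Surgeons report operative complications separately. There is no inferential testing, AEs will be listed, and Baseline is meant to fall close to surgery. A Baseline anchor also suits late drug effects, which Protocol 1.2.6 says cannot be excluded. All of this stands and limits the point to supporting tables. It does not supply the missing split: a listing gives no percentages by arm and period, and the wait remains unbounded.

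A reader might infer more than the documents support:

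- **That the arm comparison is biased.** This needs waits, pre-operative AE rates or late consent to differ by arm. The documents report no such difference, and subjects, investigators and surgeons are blinded to parent treatment.
- **That the complication endpoint is contaminated by the wait.** Its timing in SAP 8.2.2 rules this out.
- **That the exclusion strips out post-operative AEs in general.** It can do so only for subjects who consent after surgery, which is off the planned route. Worsened events are counted and the others are still followed. Whether the exclusion reaches the complication table is an ambiguity, not a stated removal.
- **That the special-interest tables were dropped because SAP 8.2.2 has no row for them.** That table has no row for general AEs either, so the absence shows little. The conflict in wording between 6.1 and 8.2.1 is what needs settling.

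**Conclusion.** The point holds, at minor severity. The general AE incidence tables, and any peripheral-sensation or sympathetic tables built the same way, combine a variable pre-operative wait with 24 post-operative weeks, and nothing in the plan separates the two. The size cannot be determined from the documents. The illustrated inflation of a 40% incidence, from 1.3 points (41.3 − 40) to 13.5 points (53.5 − 40), rests wholly on assumed waits, rates and rate ratios. Its upper end needs a 12-week wait and a pre-operative AE rate as high as the post-operative one.

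The late-consent issue is secondary. It is first an inconsistency between criterion 3 and the consent and Baseline rules, and it has a numerical effect only if such subjects exist. Their number is not given.

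**What to change.** 1. Keep the Baseline-anchored AE table for late drug effects. Add a split of AE incidence, and of any special-interest tables, by onset before Day 1 versus Day 1 through Week 24.
2. Report the Baseline-to-surgery interval by arm, and the number of subjects who consented after surgery.
3. Reconcile criterion 3 with Protocol Table 1, Protocol 6.1 and SAP Appendix 1.1. If any subject consented after surgery, anchor that subject's AEs to the date of the joint replacement. Do not apply the ongoing-from-parent-study exclusion to AEs with onset on or after that date. Take those AEs from the parent-study data, with a source flag, for the AE and complication summaries.
4. Reconcile SAP 6.1 with SAP 8.2.1 on whether the special-interest AE tables will be produced.

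The split costs one extra table layout from data already collected, plus a short interval summary. Bringing in parent-study AEs is a modest programming step with a check against double counting, and it is not needed if no subject consented after surgery. The two reconciliations are wording changes.
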